8.2 Safety

8.2.1 Safety Parameters

Safety parameters include all protocol-defined adverse events as well as revision and/or removal rates. For details regarding protocol-defined adverse events, see Section 6.1.

8.2.2 Safety Analyses

The frequency and percentage of all protocol-defined adverse events will be tabulated.

The all cause revision/removal rates for the Triathlon TS Total Knee System with Triathlon Tritanium Cone Augments will be calculated.

The Kaplan-Meier survival curve of all cause revision/removal will be displayed using SAS/PROC LIFETEST.

For details regarding protocol-defined adverse events, see Section 6.1.

8.3 Missing Data

No missing data will be imputed.

8.4 Statistical Methodology

8.4.1 Data Summary

Descriptive statistics will be computed for all baseline conditions and demographic parameters. That is, for continuous data, the N, mean, median, standard deviation, minimum and maximum will be computed. For categorical data, the frequency will be computed. The data will be presented by appropriate subgroups (e.g., center).

For all additional data collected that are not required for direct support of a study objective, data will be summarized according to visit. For parameters represented by continuous variables (e.g., ROM), the summaries will consist of the N, mean, median, standard deviation, minimum, and maximum values. For categorical variables (e.g.,gender), the frequency and percentage in each category will be presented.

A two way table of preoperative AORI classification by femoral or tibial cone augment size will be presented.

A table of shin pain by thigh pain will be created separately for cases with femoral cone augment implanted only, tibial cone augment implanted only, and both femoral cone augment and tibial cone augment implanted at preoperative, 6 weeks, 2 years, and 5 years.

LEAS at 2 years will be compared to the Triathlon TS Outcomes Study as reported at 2 years postoperative, adjusted by preoperative LEAS, age, gender, and BMI, if applicable. The improvement from preoperative visit to postoperative visits will be compared with the Triathlon TS Outcomes Study, if applicable.

The HSS Patella Score at 2 years postoperative will be compared to the Triathlon TS Outcomes Study as reported at 2 years postoperative, adjusted by preoperative HSS Patella Score, age, gender, and BMI, if applicable. The improvement from preoperative visit to postoperative visits will be compared with the Triathlon TS Outcomes Study if applicable.

Statistical analyses including T-test, Wilcoxon test or Chi-square tests will be utilized for comparing the applicable surgical data collected from Triathlon TS Outcomes Study.

For radiographic data, data will be presented according to visits for available parameters. Frequency and percentage will be computed for radiolucency according to visit. Lists will be generated for migration over time. Radiographic failure will be evaluated, where radiographic failure is defined as at least 2 mm radiolucency in all zones within a single view. Radiographic failure due to device migration will be evaluated by the independent reviewer. Documentation of statistical analyses utilizing SAS[®] software version 9.1.3 or higher.

8.4.2 Sample Size Justification

For primary efficacy objective, based on the literature review^{1,2}, it is reasonable to have a reference value of 97.2% for success rate at 2 years. A case success at 2 years is defined as no incidence of revision/removal of femoral or tibial cone augment for aseptic loosening within 2 years.

Based on Triathlon TS Outcome Study, it is reasonable to assume the expected success rate at 2 years is 98.8%, 100 cases will be needed to have a power of 80% to detect that the 2 year success rate is non-inferior to 97.2% with a margin of 2.5% at 5% significance level. After factoring a 30% lost to follow-up rate, a total of 145 cases will be needed.

For exploratory efficacy objective among cases receive the Triathlon TS Total Knee System with a Triathlon Tritanium Central Femoral Cone Augment, based on the existing data of this study for non-femoral central cone, it is reasonable to have a reference value of 86 for the mean of KSS Objective Knee Score at 2 years postoperative, with a standard deviation of 10, 32 cases will be needed to have a power of 80% to identify the mean of KSS Objective Knee Score at 2 years postoperative is Non-Inferior to 86 with a noninferiority margin of 5 at 2.5% significance level. After factoring a 30% attrition rate, a total of 46 cases will be needed.

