1.1 Background

Reconstruction of large metaphyseal defects, severe bone loss and achieving lasting component fixation in the femur or tibia during revision total knee arthroplasty (TKA) are clinically challenging problems^{2,4}. Modern knee systems provide a modular approach to reestablishing the femoral and tibial anatomy, and implant selection should be based on the complexity of the reconstruction⁵. Various options are available for the management of small bone defects which include bone grafts, metal augments, and extended stems. To address larger defects categorized as Type II and Type III based on Anderson Orthopaedic Research Institute's (AORI) classification^{6,7}, metaphyseal cones or sleeves have shown to provide stable fixation and early structural support^{4,8}.

There have been a few studies showing early results for revision TKA using either tantalum cones or metaphyseal sleeves. In a retrospective study, Lachiewicz et al.² reported on 27 revision TKA procedures, including nine femoral cones and 24 tibial cones addressing Type IIB and III AORI bone defects. Overall there were two failures, one for infection and the second for aseptic loosening (3.7%) by 25 months post-op. All other cone augments showed evidence of osseointegration at the latest follow-up (average of 3.3 years). Additionally, Aggarwal et al.¹ retrospectively reviewed 104 revision TKAs in 103 patients needing metaphyseal sleeves. Of all the cases included in the analysis, two were revised for aseptic loosening at six months postoperatively. With an average follow-up of 43 months, the remaining 102 knees showed good evidence of osseointegration.

The Triathlon TS Total Knee System was developed as platform knee technology for Stryker Orthopaedics. The Triathlon TS Total Knee System, cleared for use under FDA 510(k) K070095 and K072221, includes femoral components fabricated from cast cobalt-chromium-molybdenum alloy, distal and posterior femoral augments, fluted stems, stem extenders, offset

adapters, tibial inserts fabricated from ultra-high molecular weight polyethylene (UHMWPE) and a patellar component also made from UHMWPE.

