8.1.4 Primary Efficacy Hypothesis

The primary hypothesis to be tested will be that the success rate at 2 years postoperative with the Triathlon Tritanium Cone Augments is not worse than 97.2% with a non-inferiority margin of 2.5%. That is, the following hypothesis will be tested:

Ho: Pt <= 97.2% - 2.5% HA: Pt > 97.2% - 2.5%

Here, Pt is the success rate at 2 years postoperative with the Triathlon Tritanium Cone Augments. A case success at 2 years is defined as no incidence of revision/removal of femoral or tibial cone augment for aseptic loosening within 2 years.

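### Does the 97.2% two-year reference count a loosening failure that the trial's own two-year endpoint would leave out?

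*Combined protocol and SAP*

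**What the plan says.** Section 8.4.2 bases the primary reference on two cited reports: "it is reasonable to have a reference value of 97.2% for success rate at 2 years". It gives neither counts nor a formula. Sections 8.1.4 and 8.4.2 define a case success as "no incidence of revision/removal of femoral or tibial cone augment for aseptic loosening within 2 years". With the 2.5-point margin the bound is 94.7%. Section 8.1.5 compares it with the lower limit of a 90% two-sided interval and names no interval method.

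Section 1.1 describes the two series. The cone report "reported on 27 revision TKA procedures, including nine femoral cones and 24 tibial cones" and had two failures, "one for infection and the second for aseptic loosening (3.7%) by 25 months post-op". The sleeve report "retrospectively reviewed 104 revision TKAs in 103 patients needing metaphyseal sleeves", of which "two were revised for aseptic loosening at six months postoperatively". Apart from these, section 1.1 reports osseointegration in the other cones at an average of 3.3 years, and says that "the remaining 102 knees showed good evidence of osseointegration" at an average of 43 months.

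The Evaluation Schedule gives the 2-year visit a window of 2 months either side. No passage applies that window to the success definition.

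**The concern.** A performance goal should count events over the same period as the endpoint compared with it. The two sleeve revisions, at six months, clearly lie inside two years. The cone failure is placed only at or before month 25. If it fell between months 24 and 25, it would lower the reference, while the same event in a study knee would be a success. Such a mismatch could only make the test easier for the device.

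One event matters because there are only three. Under the averaging that reproduces the plan's figure, the cone failure supplies about two thirds of the 2.8% failure rate, and the non-inferiority decision at the planned size turns on one or two failures.

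**Working it through.** **Inputs.** Section 1.1: 1 loosening failure in 27 (cones) and 2 in 104 (sleeves). Section 8.1.4: margin 2.5 points. Section 8.4.2: expected success 98.8%, 100 evaluable cases, 145 enrolled with 30% loss. 145 × 0.70 = 101.5, taken as 102.

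**1. The plan's figure.** 1/27 = 3.70% and 2/104 = 1.92%.
- Unweighted mean: (3.70% + 1.92%)/2 = 2.81%, so success is 97.19%, which rounds to the stated 97.2%.
- Weighted by knees: 3/131 = 2.29%, so success is 97.7%, which does not match.

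The unweighted mean is thus the likely derivation, and it includes the cone failure. That failure's share is (3.70%/2)/2.81% = 1.85/2.81 = 66%.

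**2. If the cone failure came after month 24.** The two-year counts become 0/27 and 2/104. Each row keeps one weighting throughout.

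| Weighting | Reference, failure counted | Reference, failure left out | Bound, failure counted | Bound, failure left out |
|---|---|---|---|---|
| Unweighted | 97.2% | 100% − 1.92%/2 = 99.04% | 94.7% | 96.54% |
| By knees | 97.7% | 100% − 2/131 = 98.47% | 95.2% | 95.97% |

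**3. Effect on the decision at 102 evaluable.** Lower limits of the 90% two-sided interval:

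| Failures | Exact | Wilson | Jeffreys | Wald |
|---|---|---|---|---|
| 0 | 97.11% | 97.42% | 98.14% | 100% |
| 1 | 95.43% | 95.72% | 96.23% | 97.41% |
| 2 | 93.96% | 94.25% | 94.68% | 95.78% |
| 3 | 92.57% | 92.87% | 93.26% | 94.31% |

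Failures allowed:

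| Bound | Exact | Wilson | Jeffreys | Wald |
|---|---|---|---|---|
| 94.7% (plan) | 1 | 1 | 1 | 2 |
| 96.54% (unweighted) | 0 | 0 | 0 | 1 |
| 95.97% (by knees) | 0 | 0 | 1 | 1 |

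One failure in 102 therefore misses both higher bounds with exact or Wilson, misses only the 96.54% bound with Jeffreys, and clears both with Wald.

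**4. Chance of passing at a true success rate of 98.8%.** With X failures distributed binomial(102, 0.012), P(X = 0) = 29%, P(X ≤ 1) = 65% and P(X ≤ 2) = 88%. Moving the bound from 94.7% to 96.54% takes the chance from 65% to 29% with exact, Wilson or Jeffreys, and from 88% to 65% with Wald.

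**5. If the failure came at or before month 24.** The counts stay at 1/27 and 2/104, the reference stays at 97.2%, and steps 2 to 4 do not arise.

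**6. What the documents say about the date.** Section 1.1 gives one time limit in a sentence about two failures, one infection and one loosening. It may be the date by which both had happened, and the later one could be the infection. The sentence calls the loosening case a failure and does not say when, or whether, the component was revised. Nothing else in the documents dates it.

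**The case for a change.** The best case for acting is that the reference leans heavily on one imprecisely dated event, that the sponsor holds the cited report and can check the month, and that a cheap safeguard exists. Loosening revisions up to month 26 would count as failures, so that an event at month 25 counts on both sides while 97.2%, 94.7% and 145 cases all stay. That rule could only add failures, so it could not favour the device. Section 6.1 already requires operative-site events to be reported whenever they occur.

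Part of this stands. The arithmetic is sound, the derivation is not written down, and a failure after month 24 would cost one allowed failure at about 102 cases under each of the four intervals, on the plan's apparent averaging.

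The safeguard is weaker than it looks. It would move the primary endpoint to suit an event whose date is unknown. It needs both series to have complete counts to month 26, and average follow-up of 3.3 years and 43 months does not show that every knee got that far. A study subject seen between months 22 and 24 has no further scheduled visit until year 5, so events up to month 26 would depend on unscheduled reporting unless contact were added or the analysis delayed.

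The reference is also imprecise in itself. Exact 95% intervals for the failure rates are about 0.1% to 19% for 1/27 and 0.2% to 6.8% for 2/104. A shift of 1.8 points (unweighted) or 0.8 points (by knees) is small beside that.

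**Conclusion.** No change to the plan follows. The documents do not establish that the reference and the endpoint cover different periods; they show only that this is possible. If the cone failure came at or before month 24, the effect is zero. If it came later, the reference on the plan's apparent averaging would be 99.0% with a bound of 96.5%, and the failures allowed at about 102 cases would drop from 1 to 0 (exact, Wilson, Jeffreys) or from 2 to 1 (Wald). These sizes assume that the unweighted mean is how 97.2% was reached, that the 2.5-point margin is kept, and that 30% of 145 cases are lost.

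What can be said without that condition is that section 8.4.2 omits its derivation. The counts in section 1.1 let a statistician rebuild it in one line, and whoever reports the result can check the month in the cited report. The bound and the success definition are fixed in advance and can be applied as written. Extending the endpoint to 26 months would exchange a clear two-year definition for one with uncertain ascertainment, to correct a discrepancy that may not exist.

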	System with at least one Triathlon Tritanium Cone Augment. The	
	clinical outcomes of Triathlon Tritanium Cone Augments will be	
	compared to published literature and data collected in the Triathlon TS	
	Outcomes Study.	
	1. Follow-up of each revision TKA case to 5 years	
Study Duration	2. Enrollment period of 48 months	
	3. Approximate 10-year total duration	
Number of Centers	8 to 12 investigational centers	
	The revision rate of the Triathlon Tritanium Cone Augments is expected	
Hypothesis	to be less than 2.8% for a septic loosening ^{$1,2$} of either the Femoral or the	
	Tibial Cone Augments at 2 years postoperative.	

	Primary:
	To evaluate the success rate of the Triathlon Tritanium Cone Augment
	with the Triathlon TS Total Knee System at 2 years postoperative,
	defined as absence of revision of the Femoral Cone Augment or Tibial
	Cone Augment for aseptic loosening.
	Secondary:
	To evaluate unexpected end-of-stem pain with regards to the
	Triathlon Tritanium Cone Augments location and severity and
Objectives	compare to published literature ³ at 2 years postoperative.
	To evaluate intraoperative bone defects using the Anderson
	Orthopaedic Research Institute (AORI) classification and correlate
	with the size and shape of cone implanted ^{6,7} .
	Exploratory:
	To evaluate the mean KSS objective knee scores at 2 years
	postoperative for cases which received the Triathlon TS Total Knee
	System with a Triathlon Tritanium Central Femoral Cone Augment.

	Function and health related quality of life (QOL) will be compared
	between the Triathlon TS with Triathlon Tritanium Cone Augments
	and published results for other revision knee systems with
	metaphyseal augments, as well as the Triathlon TS Outcomes
	Study using the following outcomes measures:
	 2011 Knee Society Score (KSS)⁹
	 Short Form-12 (SF-12)
	 Lower Extremity Activity Scale (LEAS)
	 Hospital for Special Surgery (HSS) Patella Score
Additional Data	 ○ EuroQuol 5D (EQ-5D)
Collection	 Follow-Up Questionnaire
	• Data collected at 6-week, 6-month, 1-year, 2-year, and 5-year
	visits will be compared to above mentioned controls with respect to
	improvement from preoperative scores.
	Radiographic stability, preoperative AORI classification and
	complications will be compared between those implanted with the
	Triathlon TS with Triathlon Tritanium Cone Augments and
	published results for other revision knee systems.
	Surgical details will be compared to data collected as part of the

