		excess of normal physiological requirements (e.g. > 30 days).
	J.	Patient has a failed unicondylar knee prosthesis.
	K.	Patient has a known sensitivity to device materials.
	L.	Patient is a prisoner.

	Primary Objective:
Statistical Methodology	 2-year success rate of the TS Total Knee System with Triathlon Tritanium Cone Augments with an endpoint of revision/removal of Femoral Cone Augment or Tibial Cone Augment for aseptic loosening will be compared with success of published literature on revision TKA with metaphyseal augments, with a 2.5% noninferiority margin. Secondary Objectives: The unexpected end-of-stem pain at 2 years will be tabulated separately for cases with femoral cone implanted only, tibial cone implanted only, both femoral and tibial cone implanted. The two way tables will have the level of shin pain as row variable and level of thigh pain as column variable. A two-way table of intraoperative AORI classification by femoral or tibial cone augment size will be presented
	 Exploratory Objective: The mean of KSS Objective Knee Score at 2 years postoperative for cases receive the Triathlon TS Total Knee System with a Triathlon Tritanium Central Femoral Cone Augment will be compared to 86 points with a 5 points noninferiority margin.

Evaluation Schedule

Evaluation	Preop X-rays (-1 yr) CRFs (-4 mos)	Intraop	6 weeks (+ 2 wks)	6 months ((+ 2 wks)	1 year (+ 2 mos)	2 years (+ 2 mos)	5 years (+ 2 mos)
Inclusion/Exclusion	x						
Demographics & Medical History	x						
Preoperative Functional Evaluation	x						
Previous Implant Information		Х					
Surgical Details		Х					
Postoperative Functional Evaluation			X	Х	Х	X	X
SF-12	Х		X	X	Х	X	X
LEAS	X		X	X	X	X	X
HSS Patella Score	X		X	X	X	X	Х
EQ-5D	X		X	X	X	X	X
Stem Tip Pain Diagram	Х*		x			х	x
*If applicable							
Radiographs:							
1. Bilateral* Anteroposterior (AP)							
X ^a . Long standing at pre-op and 6 weeks							
X ^b . Standard at 1 year, 2 years, and 5							
years	Va		Va	Yþ	Vþ	Yb	Yb
2. Mediolateral (ML)	~				•		•
3. Merchant (30° flexion)							
*Bilateral AP x-rays are preferred. Unilateral AP x-							
rays may be submitted if bilateral images are not							
available.							

X: Evaluation is required for all cases.

Functional Evaluation: The Functional Evaluations include the 2011 KSS, a standardized instrument with both surgeon completed, and patient reported sections that evaluate function, satisfaction, pain and motion.

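### Does the underived 97.2% reference rate leave the primary pass line in doubt?

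*Combined protocol and SAP*

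**What the plan says.** Section 8.4.2 rests the benchmark on two literature references and concludes that "it is reasonable to have a reference value of 97.2% for success rate at 2 years". The Study Synopsis (Hypothesis) gives the same figure as a revision rate, expected "to be less than 2.8% for a septic loosening", citing the same two references. The synopsis (Statistical Methodology) names the comparator as "published literature on revision TKA with metaphyseal augments, with a 2.5% noninferiority margin".

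Section 1.1 supplies the data. It treats the two device types together: "metaphyseal cones or sleeves have shown to provide stable fixation and early structural support". The cone series "reported on 27 revision TKA procedures, including nine femoral cones and 24 tibial cones addressing Type IIB and III AORI bone defects", and "Overall there were two failures, one for infection and the second for aseptic loosening (3.7%) by 25 months post-op". The sleeve series "retrospectively reviewed 104 revision TKAs in 103 patients needing metaphyseal sleeves", of which "two were revised for aseptic loosening at six months postoperatively".

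Sections 8.1.4 and 8.1.5 turn the reference into one rule: non-inferiority is supported if the lower limit of a 90% two-sided interval exceeds 97.2% − 2.5% = 94.7%. No interval method is named.

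**The concern.** With no concurrent control, the reference rate and margin are the whole comparison. A reader who takes the counts in section 1.1 and divides does not get 97.2% from the cone series, the sleeve series or all 131 knees together, and section 8.4.2 does not say how the figure was reached. The device under study is a cone, yet most of the benchmark cases are sleeves.

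At around 100 evaluable cases one failure more or less decides the primary result, so a shift of a point or so in the reference could reverse it. If the documents left open which series counts, the same data could be non-inferior against one benchmark and not against the other, and nobody could tell whether the line was reasonably placed.

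**Working it through.** **Inputs.** Section 1.1: 1 aseptic-loosening failure in 27 (cones) and 2 in 104 (sleeves). Sections 8.1.4 and 8.1.5: margin 2.5 points, 90% two-sided interval. Section 8.4.2: assumed success 98.8%, 100 evaluable cases, 145 enrolled, 30% loss (145 × 0.70 = 101.5 evaluable).

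**Reproducing 97.2%.**

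- Cones: 26/27 = 96.30%
- Sleeves: 102/104 = 98.08%
- Pooled by cases: 128/131 = 97.71%
- Unweighted mean: (96.30% + 98.08%)/2 = 97.19%, which rounds to 97.2%
- As failure rates: (3.7% + 1.9%)/2 = 2.8%, the synopsis figure

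So the reference can be recovered from the two cited series. That it was derived this way is an inference from the match.

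**Pass line.** Each reference less 2.5 points gives a bound. The allowance is the largest number of failures whose 90% two-sided lower limit still exceeds it. The exact lower limit for x successes in n is the 5% quantile of Beta(x, n − x + 1). At n = 100, for 0/1/2/3 failures:

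- Exact: 97.05 / 95.34 / 93.84 / 92.43%
- Wilson: 97.37 / 95.64 / 94.13 / 92.73%
- Wald: 100 / 97.36 / 95.70 / 94.19%

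Failures allowed (the same at n = 100, 101 and 102):

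| Benchmark | Bound | Exact | Wilson | Wald |
|---|---|---|---|---|
| Plan (97.2%) | 94.7% | 1 | 1 | 2 |
| Pooled by cases | 95.2% | 1 | 1 | 2 |
| Cones only | 93.8% | 2 | 2 | 3 |
| Sleeves only | 95.6% | 0 | 1 | 2 |

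**Equal versus case weighting.** The first two rows agree under every method. With exact limits, 98.8% true success and n = 100, both pass with probability P(0 or 1 failure) = 0.299 + 0.363 = 66.2%.

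The number evaluable will vary. Let each of 145 cases be retained independently with probability r. The chance that the two bounds give different verdicts is the sum over n of the Binomial(145, r) weight times P(lower allowance < failures ≤ higher allowance), with failures Binomial(n, 0.012).

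- r = 0.70 (planned): 6.5% exact, 2.1% Wilson, 1.1% Wald. With the pooled bound unrounded (95.21%) the exact figure is 8.3%.
- r = 0.80: 11.5%, 19% and 9%.

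**One series only.** Under exact limits the 2/1/0 pattern for cones, plan and sleeves occurs only at n = 100 to 105. At n = 100 the 2 clears the cone bound by 93.84 − 93.80 = 0.04 points.

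**The case for a change.** The best case for a change is that a single-arm threshold should be auditable and this one is not. If the rates were averaged, 27 procedures count as much as 104 knees, and the result is slightly more lenient than pooling (94.7% against 95.2%). If cones alone are the proper comparator, the bound is 93.8%, and exactly 2 failures (probability 21.8% at n = 100 and 98.8% success) fails as written but passes there under exact or Wilson limits. Against sleeves alone, exactly 1 failure (36.3%) passes as written but fails under exact limits. The probability of success under exact limits then runs from 88.1% (cones) to 29.9% (sleeves). Only three events support a benchmark treated as known.

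The cone failure is also dated only as by 25 months. If it fell after 24 months, the pooled rate would be 129/131 = 98.5% and the bound about 96.0%, with no failures allowed under exact or Wilson limits.

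The arithmetic stands, as does the missing derivation. The step to a doubtful pass line does not. Sections 8.4.2 and the synopsis cite both series for the figure, and the stated comparator is metaphyseal augments in general, so a single-series benchmark discards a source the plan chose to use. A fixed literature goal is inherent in this design, and wide intervals around small series do not make the goal an error. The dating question cannot be settled from these documents, and it weakens any alternative threshold built on the same counts: without that failure the cone-only bound would be 97.5%, stricter than the plan's rather than looser.

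**Conclusion.** No change follows. Section 8.4.2 omits the arithmetic behind 97.2%, but the figure is recoverable from the two series it cites and agrees with the synopsis. The one real ambiguity is equal weighting against weighting by cases. It leaves the allowance unchanged at 100 to 102 evaluable cases under all three interval methods, and changes the verdict in about 1% to 8% of trials at the planned retention. At 80% retention this rises to between 9% and 19%, which is not negligible, but the rule to be applied is still the stated one.

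Study data already exist (section 8.4.2 draws on them for the exploratory objective), so moving the reference now would be worse than leaving it. Reporting the result against further thresholds and labelling it benchmark-sensitive is a matter of preference. A line giving the counts and weighting would be good drafting and can go in the study report. The unnamed interval method affects the allowance more (1 failure exact or Wilson, 2 Wald at the stated bound), but that is a separate matter from where the reference was set.

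This rests on all 27 and 104 cases counting in the 2-year denominators (section 1.1 gives only average follow-up), on all three failures counting as 2-year failures, and on the plan's own 98.8% and independent retention for the probabilities.

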2.3 Number of Subjects

Cases will be enrolled until at least 145 cases have received the Triathlon TS Total Knee System with a Triathlon Tritanium Cone Augment. Additionally, between 40 - 50 cases (within the study population) must receive the Triathlon TS Total Knee System with a Triathlon Tritanium Central Femoral Cone Augment.

3 Device Description

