8.1.5 Primary Efficacy Analysis

A 90% two-sided confidence interval will be computed for the success rate at 2 years. If the lower bound of the confidence interval is greater than 94.7%, then the non-inferiority hypothesis will be supported; that is the 2 year success rate is non-inferior to 97.2% with a margin of 2.5%. If the lower bound of the confidence interval is greater than 97.2% then it is supported that the 2 year success rate is superior to 97.2%.

The Kaplan-Meier survival curve of revision/removal of femoral or tibial cone augment will be displayed using SAS/PROC LIFETEST.

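### At about 100 evaluable cases the primary decision rule cannot give 80% power with 5% error, and at exactly 2 failures the verdict depends on an interval method the plan does not name.

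*Combined protocol and SAP*

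**What the plan says.** Section 8.1.4 sets the hypotheses: "Ho: Pt <= 97.2% - 2.5% HA: Pt > 97.2% - 2.5" per cent, so the null success rate is 94.7%. Section 8.1.5 gives the decision rule. "A 90% two-sided confidence interval will be computed for the success rate at 2 years", and "If the lower bound of the confidence interval is greater than 94.7%, then the non-inferiority hypothesis will be supported". It adds a second claim, made against the reference rate itself: "If the lower bound of the confidence interval is greater than 97.2% then it is supported that the 2 year success rate is superior". No section says how the interval is calculated. PROC LIFETEST is named only for displaying the survival curve.

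Section 8.4.2 assumes a true rate of 98.8% and states that "100 cases will be needed to have a power of 80% to detect that the 2 year success rate is non-inferior to 97.2" per cent, the full target being "non-inferior to 97.2% with a margin of 2.5% at 5% significance level". It continues: "After factoring a 30% lost to follow-up rate, a total of 145 cases will be needed". Section 2.3 makes 145 a minimum: "Cases will be enrolled until at least 145 cases have received the Triathlon TS Total Knee System". Under section 8.4.4 the primary analysis uses only cases available for evaluation at 2 years, so the planned evaluable number is about 100.

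**The concern.** Success is a yes/no outcome per case, and very few failures are expected: 100 × 0.012 = 1.2 at the assumed rate and 100 × 0.053 = 5.3 at the null. With counts this small, a confidence-interval rule can change only in whole failures, and standard interval methods disagree about where the cut-off falls. A sample size taken from a smooth approximation may then promise power and error that the actual rule cannot deliver together.

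Two things are at stake. The stated power may be too high for any rule that respects the 5% level. And if the failure count lands where the methods disagree, the study's only primary hypothesis passes or fails on a choice the plan has not made, in an open-label single-arm study.

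**Working it through.** **Inputs.** Null rate 97.2% − 2.5% = 94.7% (8.1.4); assumed true rate 98.8%, 100 evaluable, 80% power, 5% level, 30% loss, 145 total (8.4.2); 90% two-sided interval, so 5% in the lower tail (8.1.5).

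**1. The plan's own figure.** A one-sample normal formula with the variance at the reference rate gives

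n = 0.972 × 0.028 × (1.645 + 0.842)² / (0.988 − 0.947)² = 100.1,

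with 79.97% power at 100. Rounding up, 101 / 0.70 = 144.3, hence 145. The arcsine formula gives 102.9 (79.0% power at 100). So 100 and 145 are not slips. The variance used is, however, neither the null's nor the alternative's; with both of those, the normal formula gives 126, and 64.8% power at 100.

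**2. The rule at 100 cases.** Let X be the number of failures, X ~ Bin(100, p).

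| Pass if | One-sided error (p = 0.053) | Power (p = 0.012) |
|---|---|---|
| X ≤ 1 | 0.0043 + 0.0242 = 2.85% | 0.2990 + 0.3632 = 66.2% |
| X ≤ 2 | 0.0285 + 0.0669 = 9.54% | 0.6622 + 0.2183 = 88.1% |

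No cut-off lies between these. Even a randomised most powerful test at exactly 5% reaches only 0.6622 + [(0.0500 − 0.0285) / 0.0669] × 0.2183 = 73.2%.

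**3. Which cut-off each interval gives.** Lower 90% two-sided limits at n = 100, to be compared with 94.7%, and the highest one-sided error over every evaluable number from 100 to 145:

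| Method | 1 failure | 2 failures | Verdict at 2 | Highest error, 100–145 |
|---|---|---|---|---|
| Clopper-Pearson | 95.34% | 93.84% | fail | 4.98% |
| Agresti-Coull | 95.28% | 93.85% | fail | 4.98% |
| Log-log | 94.93% | 93.74% | fail | 4.98% |
| Logit | 94.99% | 93.80% | fail | 5.2% |
| Wilson | 95.64% | 94.14% | fail | 6.2% |
| Mid-P | 95.95% | 94.42% | fail | 7.6% |
| Jeffreys | 96.16% | 94.58% | fail | 8.5% |
| Arcsine | 96.71% | 95.06% | pass | 10.8% |
| Wald, continuity-corrected | 96.86% | 95.20% | pass | 11.5% |
| Wald | 97.36% | 95.70% | pass | 16.0% |

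All ten pass at 1 failure and all fail at 3. P(X = 2) at a true 98.8% is 21.8%.

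**4. Other evaluable numbers (Clopper-Pearson, true rate 98.8%).** The rule allows 1 failure for n = 88–116, 2 for 117–143 and 3 for 144–170. With 145 enrolled:

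| Loss | Evaluable | Power |
|---|---|---|
| 30% | 101 | 65.8% |
| 25% | 108 | 62.8% |
| 20% | 116 | 59.4% |
| 15% | 123 | 81.6% |
| 10% | 130 | 79.4% |
| 5% | 137 | 77.3% |
| 0% | 145 | 90.2% |

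Power is not monotone in n: it falls within each block and jumps when one more failure is allowed.

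**5. The superiority claim (lower bound above 97.2%).** At 0 failures in 100, Clopper-Pearson gives 0.05^(1/100) = 97.05%, not superior, and Wilson gives 97.37%, superior. Wald claims superiority even at 1 failure (97.36%). If the true rate were exactly 97.2%, the false-claim rate would be 0.972^100 = 5.84% for Wilson and P(X ≤ 1) = 22.7% for Wald. With Clopper-Pearson the claim first becomes possible at n = 106 with no failures, and at n = 168 with one.

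**The case against.** The strongest reply is that the sample-size arithmetic is sound: 100 and 145 both reproduce. That stands. It shows the number came from a recognised approximation, not that the rule in 8.1.5 behaves as the approximation predicts.

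A second reply is that 5% may be meant as a nominal level. Under a Wald interval, power would then be 88.1%, above the target. The attained error would be 9.54%, though, almost double the stated level. The claim here is about power and error together, and on that reading it is unaffected.

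Third, 145 is a floor and 30% a cautious loss rate, so more than 100 cases may be evaluable. That is fair, and exact power does reach 80% or more at 117–128 and at 144–145. But it is lower at 108 and 116 than at 100, and the plan's own scenario is about 100.

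Fourth, holding error at or below 5% at every evaluable number is stricter than the documents require. Wilson, for instance, exceeds 5% at only 11 of the 46 sizes from 100 to 145 and is at 2.85% at n = 100. This has some force: naming any reasonable interval in advance would remove the ambiguity. It would not restore 80% power at 100.

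Finally, silence on the method does not show that it will be chosen after the data are seen. True; the point is that nothing in the plan prevents it. Kaplan-Meier limits from PROC LIFETEST would not settle the matter either. Without censoring, 2 failures in 100 gives 95.72% on the log scale (pass) and 93.74% on the log-log scale (fail).

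**Conclusion.** The concern holds. At 100 evaluable cases and a true rate of 98.8%, none of the ten intervals combines 80% power with one-sided error within 5%. Nor can any valid 5% test on the 2-year failure count, since the ceiling is 73.2%. If the gap is filled with an interval that controls error, power is about 66%. If it is filled with a Wald-type or arcsine interval, error is about 9.5%; the inflated error arises only in that case. The verdict depends on the unnamed method when there are exactly 2 failures, a 21.8% chance. The superiority sentence has the same weakness, and with the exact interval it cannot be met at 100 cases at all.

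These figures treat cases as independent with a common success rate and take the plan's 98.8% as given. The defect should be corrected before 2-year outcomes are known, because it affects the primary conclusion.

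**What to change.** - **Section 8.1.5:** name the interval. It should keep one-sided error at or below 5% at every evaluable number from 100 to 145. Clopper-Pearson does. Wilson, mid-P, Jeffreys, arcsine and both Wald forms do not, and logit goes slightly over (5.2%).
- **Section 8.4.2:** replace the single 80% with exact power over the evaluable range. For Clopper-Pearson: 71.5% at 88, falling to 66% at 100 and 59% at 116; 80–83% at 117–128; 75–80% at 129–143; about 90% at 144–145. State that exact power is not monotone in n, and give no single minimum n as a threshold.
- **Superiority sentence in 8.1.5:** delete it, or state that with the exact interval it cannot be met at 100 cases, needs no failures at 106–167, and allows one failure only from 168.

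This costs wording only and no extra patients. The price is a less favourable stated power near 100 evaluable cases. Naming the interval does not raise that power. If the sponsor wants 80% under the exact rule at 30% loss, the first evaluable number that gives it is 117 (83.3% power, 4.92% error), or 117 / 0.70 = 167.1, so 168 enrolled. Power dips below 80% again at 129–143, so 168 is not a safe minimum.
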